7.1.5.2. Incomplete Dates

If the onset date of the AE is incomplete and the AE stop date is not prior to the first dosing date of study drug, then the month and year (or year alone if month is not recorded) of onset determine whether an AE is treatment emergent. The event is considered treatment emergent if both of the following 2 criteria are met:

- The AE onset is the same as or after the month and year (or year) of the first dosing date of study drug, and
- The AE onset date is the same as or before the month and year (or year) of the date corresponding to the cutoff date of TEAE period, which is defined as the 70 days after the study drug last dose date or the day before initiation of new anticancer therapy including SCT (whichever is earlier)

An AE with completely missing onset and stop dates, or with the onset date missing and a stop date later than the first dosing date of study drug, will be considered to be treatment emergent. In addition, an AE with the onset date missing and incomplete stop date with the same or later month and year (or year alone if month is not recorded) as the first dosing date of study drug will be considered treatment emergent.

In case when the AE onset date is incomplete and needs to be imputed, the following algorithm will be followed:

- If the day is missing but the month and year are available, then the imputed day will be the first dosing date if they have the same month and year, or the first day of the month otherwise.
- If the day and month are missing but year is available, then the imputed day and month will be the first dosing date if they have the same year, or 01Jan otherwise.

7.1.6. Summaries of Adverse Events and Deaths

Treatment-emergent AEs will be summarized based on the Safety Analysis Set.

7.1.6.1. Summaries of AE incidence in Combined Severity Grade Subsets

A brief, high-level summary of the number and percentage of patients who experienced at least 1 TEAE in the categories described below will be provided by treatment group.

The number and percentage of patients who experienced at least 1 TEAE will be provided and summarized by SOC, PT, and treatment group.

- TEAEs
- TEAEs with Grade 3 or higher
- TE treatment-related AEs for any study drug and for each study drug
- TE treatment-related AEs with Grade 3 or higher for any study drug and for each study drug
- TE SAEs
- TE treatment-related SAEs for any study drug and for each study drug
- TEAEs leading to dose reduction of azacitidine
- TEAEs leading to discontinuation of any study drug and for each study drug
- TEAEs leading to death

Multiple events will be counted only once per subject in each summary. Adverse events will be summarized and listed first in alphabetic order of SOC and then by PT in descending order of frequencies in magrolimab + azacitidine treatment arm within each SOC. For summaries by severity, the most severe grade will be used for those AEs that occurred more than once in a given subject during the study.

In addition to the above summary tables, all TEAEs, TEAEs of Grade 3 or higher, TE SAEs and TEAEs leading to death will be summarized by PT only in descending order of frequencies in magrolimab + azacitidine treatment arm.

In addition, data listings will be provided for the following:

- All AEs, indicating whether the event is treatment emergent
- All SAEs
- All Deaths
- All SAEs leading to death
- All AEs with severity of Grade 3 or higher
- All AEs leading to discontinuation of study drug
- All AEs leading to dose reduction of azacitidine
- TEAEs leading to dose delay or interruption of study drug

A summary (number and percentage of patients) of deaths will be provided by treatment group. Summary will include the following categories:

- All deaths
- Deaths within 30 days of the first dosing of study drug
- Deaths within 30 days of the last dosing of study drug
- Deaths within 60 days of the first dosing of study drug
- Deaths within 70 days of the last dosing of study drug
- Deaths beyond 30 days of the last dosing of study drug
- Deaths beyond 70 days of the last dosing of study drug

7.1.7. Additional Analysis of Adverse Events

7.1.7.1. Treatment-Emergent Adverse Events (TEAE) of Special Interest

Number and percentage of subjects with the following AEs of special interest will be summarized by PT:

- Anaemia (MST Anemia Extravascular Transient Hemolysis)
- Infusion Related Reaction (IRR) (SMQ-Hypersensitivity Narrow Terms) + within one day of latest infusion
- Transfusion reactions due to magrolimab interference with RBC typing (Gilead's MST)
- Thromboembolic Events (SMQ- Embolic and Thrombotic Events Broad Terms)
- Pneumonitis (SMQ- Interstitial Lung Disease Broad Terms)

Number and percentage of subjects with the following AEs of special interest will also be summarized by first AE onset time within 2 weeks, >2 weeks to 2 months, >2 months to 6 months, >6 months to 12 months, and >12 months of first dosing of any study drug:

- Anaemia
- IRR
- Transfusion reactions due to magrolimab interference with RBC typing
- Thromboembolic Events
- Pneumonitis

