1.2. Study Design

This is a Phase 3, randomized, double-blind, placebo-controlled multicenter study investigating magrolimab + azacitidine compared with azacitidine + placebo in previously untreated patients with intermediate/high/very high risk MDS by IPSS-R. The primary endpoints are CR rate and OS. Patients will be randomized in 1:1 ratio to receive either magrolimab + azacitidine (experimental arm) or azacitidine + placebo (control arm). Randomization will be stratified by 3 factors: 1) geographic region (US versus ex-US sites); 2) cytogenetic risk status (very good/good/intermediate versus poor/very poor versus unknown) according to IPSS-R {Greenberg 2012}; and 3) percentage of bone marrow blasts ($\geq 10\%$ versus < 10% blasts).

The primary analysis of CR rate will be conducted 8 months after 348 patients are randomized. Patient participation will include screening, treatment, and follow-up. Screening will last up to 30 days before the first dose of study treatment, during which time the patient's eligibility and baseline characteristics will be determined. Patients will receive study treatment per the dose schedule in Table 1-1. No cross-over between arms is allowed. Study treatment may be continued until disease progression (including treatment failure by International Working Group [IWG] 2006 criteria or relapse after partial/complete remission [PR/CR]), loss of clinical benefit, or unacceptable toxicities occur. In case patients discontinue the study treatment due to reasons other than disease progression, patients will be followed up for response assessments until documented disease progression occurs. For patients who come off the study treatment to receive a stem cell transplant (SCT), follow-up for response assessment and collection of SOC bone marrow biopsy/aspirate results will continue until documented disease progression occurs or start of new anticancer therapy (excluding SCT), whichever occurs first. All participants will be followed for survival until death, withdrawal of consent, or the end of the study, whichever occurs first. For participants who are lost to follow-up or withdraw consent, study staff may use public records (eg, public health records) to obtain information about survival status where allowable by local regulation.

The study treatments within each arm are described in Table 1-1:

		Dose Sche	dule (Day pe	r 28-day Cycle)
Treatment Arms	Drug/Dose/Route	Cycle 1	Cycle 2	Cycle 3+

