3.1.2. Safety Analysis Set

The Safety Analysis Set includes all randomized patients who took at least 1 dose of any study treatment, with treatment assignment designated according to the actual treatment received. This is the primary analysis set for safety analyses.

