7.1.5. Treatment-Emergent Adverse Events

7.1.5.1. Definition of Treatment-Emergent Adverse Events

Treatment-emergent adverse events (TEAEs) are defined as any AEs with an onset date on or after the study drug start date and no later than 70 days after the study drug last dose date or the day before initiation of new anticancer therapy including SCT (whichever is earlier). If the AE onset date is on or before the last dose date, the AE is considered as TEAE regardless of the start of new anticancer therapy.

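### Special-interest adverse events by onset window have no window-specific denominator: late rows understate late risk, and arms compare fairly only if observation time is equal

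*SAP*

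**What the plan says.** SAP 7.1.7.1 lists five special-interest topics: anaemia, infusion-related reactions, transfusion reactions, thromboembolic events and pneumonitis. It then plans a second table of counts and percentages, which "will also be summarized by first AE onset time within 2 weeks, >2 weeks to 2 months", and onward. The windows start at first dose, and the last two are ">6 months to 12 months, and >12 months of first dosing of any study drug". SAP 7.1.7.2 uses the same windows for immune-mediated events. Neither section states a denominator for a window.

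The nearest statement is in SAP 7.1.6: "Treatment-emergent AEs will be summarized based on the Safety Analysis Set". SAP 3.1.2 defines that set: "The Safety Analysis Set includes all randomized patients who took at least 1 dose of any study treatment".

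Observation for a treatment-emergent event is limited. Under SAP 7.1.5.1 the onset must be "no later than 70 days after the study drug last dose date or the day before initiation of new anticancer therapy including SCT". The first of these two dates applies. There is one exception: an event starting on or before the last dose counts even if new therapy has already begun. Treatment length is not fixed. SAP 1.2 says "Study treatment may be continued until disease progression", loss of benefit or unacceptable toxicity.

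Neither document plans a number at risk, a person-time rate, an exposure-adjusted rate or a cumulative incidence for adverse events. Elsewhere the SAP does restrict denominators when it means to: laboratory abnormalities (7.2.2.2) are divided by participants with postbaseline values in the relevant period.

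**The concern.** Participants leave the TEAE period at very different times, through death, end of treatment plus 70 days, or new therapy. If every window is divided by all treated participants, the rows beyond 6 and beyond 12 months count people who could no longer contribute a first event. These are people no longer observed, and people who already had the event.

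Each late percentage then mixes two things: how often the event starts late, and how many participants were still there to have it. A reader who takes the row as late risk gets too low a figure. A reader who compares arms may see a difference, or miss one, because one arm was observed for longer. This matters most for events that can start late, such as thromboembolic events, pneumonitis and immune-mediated events. For these, timing is the question the table is meant to answer.

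**Working it through.** The documents give no figure for these tables, so there is nothing to reproduce. The steps below measure how large the effect could be.

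**1. Bound from the plan's own inputs.** SAP 1.3 and protocol 8.1 assume median OS of 18 months (control) and 25.4 months (experimental). Exponential survival is my assumption. The share alive at t months is exp(−ln2 × t / median).

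- 6 months: 79.4% control, 84.9% experimental.
- 12 months: 63.0% control, 72.1% experimental.

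The TEAE period cannot outlast death. So at least 37% (control) and 28% (experimental) of an all-treated denominator could not contribute to the last row, before any treatment stop is counted.

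**2. Illustration with treatment stop.** Assumptions, none from the documents:

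- the same first-event hazard in both arms, h = 0.02 per month
- exponential treatment time, median 6 months (control) or 9 months (experimental)
- observation until 70 days after treatment stop (70 / 30.4375 = 2.30 months) or death, with new therapy and data cutoff ignored.

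Let d = ln2 / OS median, s = ln2 / treatment median and k = h + d + s. For t > 2.30, the share observed and event-free at t is R(t) = exp(2.30 s) × exp(−k t). The crude share with first onset between a and b is (h / k) × [R(a) − R(b)].

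- Control: d = 0.0385, s = 0.1155, k = 0.1740. R(6) = 45.9%, R(12) = 16.2%.
- Experimental: d = 0.0273, s = 0.0770, k = 0.1243. R(6) = 56.6%, R(12) = 26.9%.

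| Window | Measure | Control | Experimental |
|---|---|---|---|
| >6 to 12 months | % of all treated | 3.4 | 4.8 |
| | % of those at risk at start | 7.4 | 8.5 |
| >12 months | % of all treated | 1.9 | 4.3 |
| | % of those at risk at start | 11.5 | 16.1 |
| Both | first events per 100 person-months | 2.0 | 2.0 |

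For the last row, control is 0.1149 × 16.2% = 1.9% and experimental is 0.1609 × 26.9% = 4.3%, a ratio of about 2.3 at identical hazards. Dividing by those at risk does not equalize the open-ended row. It gives h / k, which still depends on how fast each arm leaves observation. Only the person-time rate recovers the common hazard.

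**3. Sensitivity.** Here a single exponential exit from observation is used, with rate l = ln2 / median. The crude share is h / (h + l) × [exp(−(h + l)a) − exp(−(h + l)b)], and the last window is taken as 12 to 48 months.

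- Median observation of 6 months in both arms, h = 1% per month: no arm difference. The >6 to 12 month row still reads 1.98%, against 4.22% of those at risk.
- Medians 6 versus 9 months, h = 1%: the last row is 1.75% versus 3.87%, a ratio of 2.2. Swapping the medians reverses it.
- Hazards from 0.5% to 2% per month: the last-row ratio stays near 2.2 for 6 versus 9 months and near 5 for 4 versus 8 months.
- Death as the only exit, h = 1%: the last row is 9.5% versus 12.7%.

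**The case against.** The table is not wrong for what it says it does. It splits first onsets by time, its rows add up to overall incidence, and no test or arm comparison is planned on it. That stands: the percentages are a valid description, and the risk lies in how they are read.

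The denominator is also an inference. SAP 7.1.6 names the Safety Analysis Set, but the onset tables are in 7.1.7. The percentages could conceivably be of subjects with the event. That stands too: all treated is the default reading, not an explicit instruction.

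The plan does give context. Exposure duration is summarized by drug (SAP 4.2.1), discontinuations with reasons (4.1), and deaths relative to first and last dose (7.1.6.1). A reader can see unequal follow-up there. However, none of it is linked to event rates. Exposure from first to last dose also leaves out the 70-day tail, new therapy and earlier events, so the number at risk cannot be rebuilt from these tables.

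A constant hazard suits several listed events poorly. Protocol 7.10.1.1 places the typical haemoglobin fall in the first 1 to 2 weeks. Infusion reactions are tied to the infusion (7.10.1.2), and thromboembolic events are sometimes early (7.10.1.3). With an assumed hazard of 10% per month for 2 months and 0.5% afterwards, and the same 6 versus 9 months, overall incidence is 19.9% versus 21.2% and the last row 0.5% versus 1.2%. The ratio persists but the absolute gap is under one point. So events that cluster early are little affected.

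**Conclusion.** The gap is real and modest. By default, the late-window percentages understate risk among those still observed. They are comparable between arms only if time in the TEAE period is the same. The understatement needs no difference between arms. On the plan's survival medians, 28% to 37% of the denominator for the last row would already have died, assuming exponential survival.

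A reader might infer that these tables will show a false late excess on magrolimab, or that they are miscalculated. The documents support neither. They give no treatment-duration figure, so 1.9% versus 4.3% is an illustration that rests on assumed durations and a constant hazard. With equal observation time there is no arm difference, and with earlier exit from the experimental arm the bias runs the other way and would hide late risk.

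The tables are descriptive. No primary result, alpha or stopping boundary is touched.

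**What to change.** In SAP 7.1.7.1 and 7.1.7.2:

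- State the denominator of the crude percentages and keep them.
- For each window, add the number of participants still in the TEAE period and without a prior event of that type at its start. Define the period as in 7.1.5.1, including its rule for events on or before the last dose, and end it at death or data cutoff if earlier.
- For each window, add first events per person-month. This column is necessary for the open-ended last window, where a number at risk alone does not remove the effect of unequal observation.
- Beside the overall crude percentage, report an exposure-adjusted incidence rate (first events divided by TEAE-period time to first event) for the special-interest and immune-mediated events. Give priority to thromboembolic events, pneumonitis and immune-mediated events. Extending this to the Grade 3 or higher tables is optional.

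The cost is SAP wording, programming from dosing, new-therapy, death and event dates already collected, and extra columns. The rates assume a roughly constant hazard within each window, which should be footnoted.

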7.1.7.2. Other Important Safety Topics

Number and percentage of subjects with the following AEs of important safety topics will be summarized by PT:

- Infections and infestations (SOC)
- Immune-Mediated Events (SMQ-Immune-mediate and autoimmune disorder Narrow Terms)
- Hemorrhages (SMQ- Haemorrhages Broad Terms)

Number and percentage of subjects with the following AEs of important safety topics will also be summarized by first AE onset time within 2 weeks, >2 weeks to 2 months, >2 months to 6 months, >6 months to 12 months, and >12 months of first dosing of any study drug:

• Immune-Mediated Events (SMQ-Immune-mediate and autoimmune disorder Narrow Terms)

7.2. Laboratory Evaluations

Laboratory data collected during the study will be analyzed and summarized using both quantitative and qualitative methods. Summaries of laboratory data will be provided for the Safety Analysis Set and will include data collected up to the last dose of study drug plus 30 days or the day before initiation of new anticancer therapy including SCT (whichever is earlier). The analysis will be based on values reported in conventional units. When values are below the LOQ, they will be listed as such, and the closest imputed value will be used for the purpose of calculating summary statistics as specified in Section 3.7.

A by-subject listing for laboratory test results will be provided by treatment group, subject ID and visit in chronological order for hematology and serum chemistry separately. Values falling outside of the relevant reference range and/or having a severity grade of 1 or higher on the CTCAE severity grade will be flagged in the data listings, as appropriate.

Plots of lab parameters will include (but not limit to) hemoglobin, platelet, and absolute neutrophil counts across time.

No formal statistical testing is planned.

7.2.1. Summaries of Numeric Laboratory Results

Descriptive statistics will be provided by treatment group for each laboratory test specified in the study protocol as follows:

- Baseline values
- Values at each postbaseline time point visit
- Postbaseline maximum value

- Postbaseline minimum value
- Change and percentage change from baseline at each postbaseline time point visit
- Change and percentage change from baseline to postbaseline maximum value
- Change and percentage change from baseline to postbaseline minimum value

A baseline laboratory value will be defined as the last measurement obtained on or prior to the date/time of first dose of any study drug. Change from baseline to a postbaseline visit will be defined as the postbaseline value minus the baseline value. The mean, median, Q1, Q3, minimum, and maximum values will be displayed to the reported number of digits; StD values will be displayed to the reported number of digits plus 1.

Median (Q1, Q3) of the observed values will be plotted using a line plot by treatment group and visit for the laboratory tests including but not limited to hemoglobin, platelet, and absolute neutrophil counts.

In the case of multiple values associated with a visit, data will be selected for analysis as described in Section 3.8.3.

7.2.2. Graded Laboratory Values

The CTCAE Version 5.0 will be used to assign toxicity grades (0 to 4) to laboratory results for analysis. Grade 0 includes all values that do not meet the criteria for an abnormality of at least Grade 1. For laboratory tests with criteria for both increased and decreased levels, analyses for each direction (ie, increased, decreased) will be presented separately.

7.2.2.1. Treatment-Emergent Laboratory Abnormalities

Treatment-emergent laboratory abnormalities are defined as values that increase at least 1 toxicity grade from baseline at any postbaseline time point, up to and including the date of last dose of study drug plus 30 days or the day before initiation of new anticancer therapy including SCT (whichever is earlier). If the relevant baseline laboratory value is missing, any abnormality of at least Grade 1 observed within the time frame specified above will be considered treatment emergent.

7.2.2.2. Summaries of Laboratory Abnormalities

Laboratory data that are categorical will be summarized using the number and percentage of patients in the study with the given response at baseline and each scheduled postbaseline time point.

The following summaries (number and percentage of patients) for treatment-emergent laboratory abnormalities will be provided by lab test and treatment group; patients will be categorized according to the most severe postbaseline abnormality grade for a given lab test:

- TE laboratory abnormalities
- TE Grade 3 or 4 laboratory abnormalities

For all summaries of laboratory abnormalities, the denominator is the number of patients with nonmissing postbaseline values up to 30 days after the last dosing date or the day before initiation of new anticancer therapy including SCT (whichever is earlier).

A by-subject listing of treatment-emergent Grade 3 or 4 laboratory abnormalities will be provided by subject ID number and visit in chronological order. This listing will include all test results that were collected throughout the study for the lab test of interest, with all applicable severity grades displayed.

7.2.3. Liver-related Laboratory Evaluations

Liver-related abnormalities after initial study drug dosing will be examined and summarized using the number and percentage of patients who were reported to have the following laboratory test values for postbaseline measurements:

- Aspartate aminotransferase (AST): > 3 times of the upper limit of reference range (ULN)
- Alanine aminotransferase (ALT): > 3 x ULN
- AST or ALT: $> 3 \times ULN$
- Total bilirubin: $> 2 \times ULN$
- AST or ALT > 3 x ULN and total bilirubin > 2 x ULN
- AST or ALT > 3 x ULN and total bilirubin > 2 x ULN and alkaline phosphatase (ALP) < 2 x ULN

The summary will include data from all postbaseline visits up to 30 days after the last dose of study drug. For individual laboratory tests, patients will be counted once based on the most severe postbaseline values. For the composite endpoints of AST or ALT and total bilirubin and ALP, patients will be counted once when the criteria are met at the same postbaseline visit date. The denominator is the number of patients in the Safety Analysis Set who have nonmissing postbaseline values of all relevant tests at the same postbaseline visit date.

A listing of patients who met at least 1 of the above criteria will be provided.

